## 5.17. Active Treatment

### 5.17.1. PriMatrix Dermal Repair Scaffold Disposition, Storage and Accountability

PriMatrix will be supplied sterile, in single use, double peel packages. For the purposes of this study, it will only be supplied in 4 x 4cm, meshed sheets with 1 sheet per box. Once received, PriMatrix should be stored at ambient conditions and has a shelf life of five years. Upon receipt, each piece will be logged on the Device Accountability Log, which will be updated each time PriMatrix is used.

The investigator will also use the device accountability log to maintain current and accurate inventory records covering the dispensing and the disposal of the study devices. At the conclusion of the study, the investigator must agree to return or destroy all study device materials as instructed by the sponsor.

### 5.17.2. PriMatrix Application Training

All investigators and Sub-investigators who will be applying PriMatrix for the trial will be trained on the use of the study device, PriMatrix, for the management of DFUs, along with other study-related procedures.

### 5.17.3. PriMatrix Application

[figure not shown]
Active treatment for this trial is PriMatrix Dermal Repair Scaffold plus secondary dressings to maintain a moist wound environment and an appropriate off-loading/protective device. After randomization, subjects assigned to the active treatment group will not perform any dressing changes but rather have their dressings changed weekly at the site.

PriMatrix and secondary dressing kits will be provided to the site. Dressing kits will be used on every subject at each dressing change. PriMatrix is ONLY to be applied to a freshly debrided ulcer with punctate bleeding and will always be handled using aseptic technique. PriMatrix will be rehydrated using a sterile saline solution at room temperature and allowed to soak for at least 2 minutes. The product should be kept in the solution until ready for application.

Once ready to apply, the product will be cut to fit the ulcer bed and applied immediately following ulcer bed preparation and hemostasis. **Note: PriMatrix should turn red as it absorbs the blood from the debrided wound bed (Figure 4).** If the PriMatrix is white, debridement is likely insufficient. As well, it is critical that the PriMatrix be in direct contact with the ulcer bed. Any air bubbles should be carefully removed by gentle rolling with a moistened cotton tip application. PriMatrix should be secured in place with adhesive strips, staples, sutures or bolster.

Figure 4: PriMatrix Application

Secondary dressings, supplied by the sponsor will include the following and should be applied as follows:

1. Non-adherent contact layer
2. Bolster of saline moistened gauze (if necessary to maintain intimate contact between PriMatrix and ulcer bed)
3. 0.9% sodium chloride gel applied over contacting non-adherent layer, if necessary to maintain a moist wound environment
4. Non-adhesive foam
5. Elastic gauze
6. Self-adherent wrap

Care should be taken to ensure that the 0.9% sodium chloride gel is applied only to the ulcer bed and not to the intact skin on the ulcer perimeter.

#### 5.17.4. PriMatrix Re-Application

PriMatrix may be reapplied a second time, if appropriate, based upon the investigator's judgement, given the clinical assessment of the ulcer. PriMatrix may be replaced if any of the following are satisfied:

- At any point, the PriMatrix is non-adherent or sloughing,

- At any point, PriMatrix is lost due to infection. The infection will be treated and resolve before PriMatrix is replaced.
- If at 4-weeks after initial application, the rate of closure is 30% or less.

**IMPORTANT: If the investigator feels a third application of PriMatrix is necessary during the trial, the Integra Clinical Research Manager or site’s CRA must be consulted prior to reapplication. Note that review of these requests may take up to 1 day, so the subject may need to return the next day for re-application.**

The reason for PriMatrix loss/reapplication will be recorded in the source document and eCRF. All PriMatrix applications must be documented on the Device Accountability Form.

When replacing PriMatrix, follow application procedures described in Section 5.17.3 of this protocol.

#### 5.18. Investigator Assessments of Ulcer Closure

**Complete wound closure** is defined as 100% re-epithelialization of the ulcer surface without detectable exudate, confirmed on 2 consecutive study visits 1 week apart (i.e., Treatment Visit where 100% re-epithelialization of the ulcer surface without detectable exudate was initially documented and the Closure Confirmation Visit). For efficacy analyses, the first date of assessment of 100% re-epithelialization of the ulcer surface without detectable exudate will be used as the date of closure.

If, at Treatment Week 12, the ulcer remains open, the investigator will document why, in his opinion, the ulcer did not close.

#### 5.19. Investigator Assessment of Ulcer Recidivism

If, following confirmed ulcer closure, the ulcer is *open* at the 4-week Follow-up visit, the investigator will document why, in his/her opinion, the ulcer re-opened. NOTE: The subject will not re-enter the study at this visit. According to section 6.2.3, subjects can re-enter the study at the *Confirmation Visit* if the wound reopens. This opportunity is not available at the 4-week Follow-up visit.

## 6. Study Activities by Phase and Visit

The schedule for the protocol-specific assessments and procedures in each phase are detailed below and are summarized in Table 3: Schedule of Events. Detailed descriptions of these assessments and procedures have been previously defined in Section 5.

The results from all of the assessments and procedures discussed in the sections below will be recorded in source documents and on the appropriate eCRF.

### 6.1. Screening Phase

#### 6.1.1. Screening Visit 1 (SV1)

At SV1, the following data will be collected, or activities performed:

1. Informed Consent and HIPAA Authorization
  - Note: Once the ICF and HIPAA authorization are signed, the screening assessments/activities identified must be completed within a **30-day window** from the date of ICF signature. Further, all screening assessments/procedures must be completed on the same day, and that date will constitute the first day of the screening phase.
2. Review of Inclusion and Exclusion criteria for eligibility
3. Demographics
4. Medical history, medications, and non-study treatments
5. Physical exam (including vital signs, height and weight)
6. Vascular perfusion
7. Perform ulcer assessments
8. Photograph the study ulcer pre-debridement
9. Perform ulcer measurements pre-debridement
10. Perform sharp debridement of the study ulcer
11. Photograph of the study ulcer post-debridement
12. Perform ulcer measurements post-debridement
13. Apply SOC treatment to the ulcer (see Section 5.11 for specific application processes)

14. Discuss treatment compliance with the subject
15. If appropriate, apply the off-loading/protective device and discuss compliance with its use
16. Document applicable Concomitant Medications noted by the subject or seen within the subject's medical records (see Section 5.14 for information on which medications require documentation).

*\*Remember to schedule the next visit for SV2, 7±3 days from SV1.*

#### 6.1.2. Screening Visit 2 (SV2)

Screening Visit 2 assessments and procedures are summarized in Table 3. At SV2 the following data will be collected, and procedures performed:

1. Review Inclusion and Exclusion criteria for continued eligibility
2. Medical Resource Utilization assessment will be performed (see Section 5.3 for specific information on how to perform this assessment).
3. Ask subject about compliance with the treatment during the previous week
4. Perform ulcer assessments
5. Photograph the study ulcer pre-debridement
6. Perform ulcer measurements pre-debridement
7. Perform sharp debridement of the study ulcer, if necessary per investigator discretion.
8. Photograph of the study ulcer post-debridement, if debridement occurred.
9. Perform ulcer measurements post-debridement, if debridement occurred.
10. Apply SOC treatment to the ulcer (see Section 5.11 for specific application processes)
11. Discuss treatment compliance with the subject
12. If appropriate, apply the off-loading/protective device and discuss compliance with its use
13. Document applicable Concomitant Medications noted by the subject or seen within the subject's medical records (see Section 5.14 for information on which medications require documentation).
14. Document any applicable AEs as noted by the subject or as documented in their medical record (see Section 5.15 for information on which AEs require documentation).

*\* Remember to schedule the next visit for Randomization/TV 1 (Day 0), 14±3 days from SV1.*

*IMPORTANT: If a subject initially fails to meet inclusion/exclusion criteria, e.g., because the ulcer is too large or is infected, and is later reconsidered for participation, the subject will be re-*

*consented and assigned a new screening number at the time of re-screening. Subjects who fail their first screening attempt may be re-screened a maximum of one time and may be entered into the study a second time if they are found to meet ALL inclusion and NO exclusion criteria.*

## 6.2. Treatment Phase

The treatment phase of the study begins when the subject completes the two-week screening phase, meets all eligibility criteria, and is randomized.

During this phase, subjects will return to the clinic every 7±3 days for up to 13 weeks or until confirmed ulcer closure. When determining the visit dates, the reference should always be to the Randomization/TV 1 (Day 0) date and not the subject's previous visit. Every attempt should be made to maintain subjects on their original treatment schedule.

The schedule of assessments for the treatment phase of the study is provided in Table 3. Detailed descriptions of these assessments and procedures have been previously defined in Section 5.

### 6.2.1. Randomization/TV 1 (Day 0)

1. Review Inclusion and Exclusion criteria for eligibility
  - *Important: The final exclusion criteria will only be determined after debridement and measurement as detailed below in this Section.*
2. Medical Resource Utilization assessment will be performed (see Section 5.3 for specific information on how to perform this assessment).
3. Ask subject about compliance with the treatment during the previous week
4. Perform ulcer assessments
5. Photograph the study ulcer pre-debridement
6. Perform ulcer measurements pre-debridement
7. Assess the ulcer for wound closure status
  - If the wound is closed, the subject is exited at this point; complete the study exit form.
8. Perform sharp debridement of the study ulcer
9. Photograph of the study ulcer post-debridement
10. Perform ulcer measurements post-debridement
11. Document ulcer size reduction
12. Complete the randomization process in the EDC system.
13. Apply either SOC or the Active treatment to the ulcer, depending on the cohort that is assigned during the randomization process (see Section 5.16 for specific application processes)

14. Discuss treatment compliance with the subject
15. If appropriate, apply the off-loading/protective device and discuss compliance with its use
16. Document applicable Concomitant Medications noted by the subject or seen within the subject's medical records (see Section 5.14 for information on which medications require documentation).
17. Document any applicable AEs as noted by the subject or as documented in their medical record (see Section 5.15 for information on which AEs require documentation).

*\* Remember to schedule the next visit for Treatment Visit Week 2, 7±3 days from Randomization/TV 1.*

#### 6.2.2. Subsequent Treatment Phase Visits (TVs 2 through 13)

The subject will return every 7±3 days for treatment visits for 13 weeks or until the ulcer is confirmed closed, whichever occurs first. The following data will be collected, and procedures performed:

1. Medical Resource Utilization assessment will be performed (see Section 5.3 for specific information on how to perform this assessment).
2. Ask subject about compliance with the treatment during the previous week
3. Perform ulcer assessments
4. Photograph the study ulcer pre-debridement
5. Perform ulcer measurements pre-debridement
6. Assess the ulcer for wound closure status
  - If criteria for complete wound closure are met at a visit, the subject will return to the clinic 7±3 days for a Confirmation Visit. If the first assessment of complete wound closure occurs at the Week 12 Visit, a Confirmation visit will be required at 7±3 days to confirm complete wound closure.
  - If criteria for complete wound closure are not met and the subject has not yet completed 13 weeks of treatment the subject will be instructed to return to the clinic in 7±3 days for the next visit in the treatment phase.
  - If criteria for complete wound closure are not met, but the subject is at Treatment Visit 13, the subject will not have items 7 through 12 below completed; the subject has completed their study requirements and is to be exited.
7. Perform sharp debridement of the study ulcer, if necessary per investigator discretion.
8. Photograph of the study ulcer post-debridement, if debridement occurred.
9. Perform ulcer measurements post-debridement, if debridement occurred.

10. Apply either SOC or the Active treatment to the ulcer, depending on the cohort that is assigned during the randomization process (see Section 5.11 or 5.17 for specific application processes of SOC or Active treatment, respectively.)
11. Discuss treatment compliance with the subject
12. If appropriate, apply the off-loading/protective device and discuss compliance with its use
13. Document applicable Concomitant Medications noted by the subject or seen within the subject's medical records (see Section 5.14 for information on which medications require documentation).
14. Document any applicable AEs as noted by the subject or as documented in their medical record (see Section 5.15 for information on which AEs require documentation).
15. investigator assessment for Complete Wound Closure (Section 5.18).

*\* Remember to schedule the next Treatment Visit (TV) if the wound is still open and the current visit is not TV 13. If the subject's ulcer is not closed at TV 13, the subject is exited; complete the study exit form. If the wound is closed on or before TV13, schedule the Closure Confirmation Visit (Section 6.2.3).*

#### 6.2.3. Closure Confirmation Visit (7±3 days after ulcer determined to be closed)

Closure Confirmation assessments and procedures are identified in Table 3.

1. Medical Resource Utilization assessment will be performed (see Section 5.4 for specific information on how to perform this assessment).
2. Perform ulcer assessments
3. Photograph the study ulcer
4. Assess the ulcer for wound closure status
5. Document any applicable AEs as noted by the subject or as documented in their medical record (see Section 5.15 for information on which AEs require documentation).

Special Instructions: If the subject returns for the closure confirmation visit AND the ulcer has reopened AND Treatment Visits 12 or 13 has not yet been reached, the subject re-enters the study at the visit after the previously scheduled next visit (e.g., if the ulcer closed at TV9, but at the Confirmation Visit the ulcer is reopen, the subject re-enters at TV11). The subject will then return every 7±3 days for up to 13 weeks or until the ulcer closure is confirmed, whichever occurs first. This process repeats until all treatment visits are used up. If the subject's wound is closed on TV 12 or 13, but is open at the Confirmation Visit they do not re-enter the study and are exited.

*\* Remember to schedule the next Treatment Visit or the 4-Week Follow-Up visit as appropriate.*

#### 6.2.4. 4-Week Follow-Up Visit (28±3 days after Confirmation Visit)

The 4-week follow-up visit assessments and procedures are identified in Table 3.

1. Perform ulcer assessments
2. Photograph the study ulcer
3. Assess the ulcer for wound closure status

#### 6.2.5. Unscheduled Visits

IMPORTANT: Unscheduled visits are to ***ONLY*** be used when a subject has an unexpected clinic visit that falls outside the next visit window. If the date of the unexpected visit falls within the window of the next regular visit, the procedures for that visit will be followed.

In the event an unscheduled visit occurs, the following will be occur:

1. Perform ulcer assessments
2. Perform sharp debridement of the study ulcer, if necessary per investigator discretion.
3. Apply either SOC or the Active treatment to the ulcer, depending on the cohort that is assigned during the randomization process (see Section 5.11 or 5.17 for specific application processes of SOC or Active treatment, respectively.).
4. Discuss treatment compliance with the subject
5. If appropriate, apply the off-loading/protective device and discuss compliance with its use
6. Document applicable Concomitant Medications noted by the subject or seen within the subject's medical records (see Section 5.14 for information on which medications require documentation).
7. Document any applicable AEs as noted by the subject or as documented in their medical record (see Section 5.15 for information on which AEs require documentation).

Important: If the Unscheduled Visit occurs between the closure visit and either the Confirmation Visit or the 4-Week follow-up visit, activities 2 through 5 will not be performed. If the wound is open at the follow-up visit, and the subject has not reached their Confirmation Visit, the subject will be re-entered per the Special Instructions in 6.2.3. SOC dressings may be applied until the next Treatment Visit. If the subject is open between the Confirmation Visit and the 4-Week follow up visit, the subject is exited.

Table 3: Schedule of Events

Procedure	Screening Phase		Treatment Phase													Follow-Up Phase		Unscheduled Visit 
	SV 1 -14±3d	SV 2 -7±3d	Randomiza- tion/ TV  1 (Day 0)	TV 2 7±3d	TV 3 14±3d	TV 4 21±3d	TV 5 28±3d	TV 6 35±3d	TV 7 42±3d	TV 8 49±3d	TV 9 56±3d	TV 10 63±3d	TV 11 70±3d	TV 12 77±3d	TV 13 84±3d	Conf Visit 7±3d After Closure	4-Week 28±3d After Confirm.	
Inf. Consent/HIPAA	X																	
Inclusion/Exclusion	X	X	X															
MRU Assessment		X	X	X	X	X	X	X	X	X	X	X	X	X	X	X		
Demographics	X																	
Medical History	X																	
Physical Exam	X																	
Vascular Perfusion	X																	
Ulcer Assessments 	X	X	X	X	X	X	X	X	X	X	X	X	X	X	X	X	X	X
Ulcer Photography	X 	X 	X 	X 	X 	X 	X 	X 	X 	X 	X 	X 	X 	X 	X 	X 	X 	
Ulcer Debridement	X	X 	X	X 	X 	X 	X 	X 	X 	X 	X 	X 	X 	X 				X 
Ulcer Measurement	X	X	X	X	X	X	X	X	X	X	X	X	X	X	X			
Control Treatment	X	X	X 	X 	X 	X 	X 	X 	X 	X 	X 	X 	X 	X 				X 
Treatment Compliance	X	X	X	X	X	X	X	X	X	X	X	X	X	X	X			X
Offloading 	X	X	X	X	X	X	X	X	X	X	X	X	X	X				X
Concomitant Meds	X	X	X	X	X	X	X	X	X	X	X	X	X	X	X			X
Adverse Events		X	X	X	X	X	X	X	X	X	X	X	X	X	X	X	X	X
Ulcer Size Reduction			X															
Randomization			X															
Active Treatment			X 	X 	X 	X 	X 	X 	X 	X 	X 	X 	X 	X 				X 
Closure Assessment			X	X	X	X	X	X	X	X	X	X	X	X	X 	X	X	

 Only to be used for a visit that falls out of range of one of the other visit windows. If the proposed Unscheduled Visit falls within the next visit window, use that visit instead of documenting an unscheduled visit.

 See important information in section 6.2.5 for guidance on Unscheduled Visits after wound closure.

 "TV" = Treatment Visit

 Study Ulcer Assessments include: 1) location 2) duration 3) size 4) exudate 5) infection 6) measurement of ulcer area

 Collect pre- and post-debridement images

 Collect pre-debridement image; if performing debridement, collect post-debridement image

 Post-application image required if randomized to PriMatrix

 Image of the closed wound area to be taken

 Debride, if necessary

 If randomized to the Standard of Care cohort

 Not required for dorsal wounds; required for plantar ulcers or lateral ulcers that would benefit from offloading

 If randomized to the Active Treatment and if necessary; see Section 5.17 for guidelines on applying PriMatrix.

 Optional application of PriMatrix. See Section 5.17 for guidelines on applying or re-applying PriMatrix

 If wound is not healed at Treatment Week 13, Investigator will document why, in his opinion, the wound did not heal.

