### 3.1. Treatment Groups (Further defined in Section 5)

- Active Treatment – PriMatrix Dermal Repair Scaffold + Standard of Care
- Control Treatment – Standard of Care

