**IMPORTANT: Sharp debridement of the study ulcer is required at SV1 and Randomization/TV 1 (Day 0).**

Sharp debridement includes removal of:

- the surrounding callus
- All non-viable tissue, as evidenced by punctate bleeding across the wound bed

At visits other than SV1 and Randomization and if needed, sharp debridement should be performed to:

- Remove callus or devitalized tissue
- Remove infected tissue

Whenever debridement is performed, details of debridement will be captured on the eCRF (i.e., reason(s) for performing debridement, type of debridement performed, and method used for debridement).

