#### 5.13. Appropriate Off-loading/Protective Device

The off-loading/protective device to be used in this study will be provided by the sponsor through a specific distributor. This off-loading/protective device will be used by all subjects with study ulcers located on the plantar or lateral surfaces of the foot (i.e., any location experiencing weight-bearing or shear forces) throughout the Screening, Treatment and Follow-up phases.

All subjects enrolled in this study are required to use the sponsor-provided off-loading/protective device for the duration of their participation (see Inclusion Criteria 9).

Off-loading devices **MUST** be continually used throughout the entire duration that the subject is enrolled in the study.

Note: If a subject is wheelchair bound, meaning that their primary form of locomotion is in the wheelchair, the offloading boot will not be required. If at any point in time, the subject ceases to be wheelchair bound, they will begin using the offloading boot if necessary.

Subjects with ulcers located on non-weight bearing surfaces (i.e., the dorsum of the foot) may use the provided off-loading boot as a protective device or may use another form of protective foot wear. The off-loading/protective device used will be noted in the eCRF.

Complete compliance information on the use of the off-loading/protective device by the subject will be collected by the study staff at each visit via subject interviews. Off-loading information collected will include type of off-loading/protective device used, number of hours per day that the device was not used since the last study visit and what proportion of that time involved weight-bearing, and any problems or issues with the off-loading/protective device. Subjects will be instructed to wear the off-loading/protective device at all times, except during sleeping, bathing, or showering.

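### Protocol 6.2.5 bars debridement and arm-assigned treatment at an unscheduled visit before Confirmation even when the ulcer is found open, and allows only SOC dressings

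*Protocol*

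**What the plan says.** - **Protocol 6.2.5 (Unscheduled Visits), the bar.** For a visit between closure and Confirmation, or between closure and the 4-week visit: "activities 2 through 5 will not be performed. If the wound is open at the follow-up visit".
- **Protocol 6.2.5, open ulcer before Confirmation.** The same paragraph continues that "the subject will be re-entered per the Special Instructions in 6.2.3. SOC dressings may be applied until the next Treatment Visit".
- **Protocol 5.9 (Sharp Debridement).** "At visits other than SV1 and Randomization and if needed, sharp debridement should be performed to" remove callus, devitalized tissue or infected tissue.
- **Protocol 3.1 and 5.17.3.** The Active arm is "PriMatrix Dermal Repair Scaffold + Standard of Care". After randomisation, "subjects assigned to the active treatment group will not perform any dressing changes but rather have their dressings changed weekly at the site". Table 3 footnote 13 describes later use as "Optional application of PriMatrix".
- **Protocol 5.13.** Off-loading devices must "be continually used throughout the entire duration that the subject is enrolled in the study".
- **Protocol 6.2.3 and Table 3, Confirmation Visit.** The five listed items are MRU, ulcer assessment, photograph, closure status and AEs. The Table 3 cells for debridement, Control Treatment, Active Treatment and Offloading are blank. Footnote 8 asks for "Image of the closed wound area to be taken". A subject whose ulcer has reopened re-enters at the visit after the one previously scheduled next; the worked example is closure at TV9 and re-entry at TV11.

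**The concern.** The bar in 6.2.5 makes sense for an ulcer that is still closed: there is nothing to debride or dress. The same paragraph then takes up the ulcer that is open and makes no exception. A site that follows it sees a diabetic foot ulcer it knows to be open and may not debride it or apply the assigned treatment. A site that follows 5.9 debrides when needed. It cannot do both.

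The arms are not affected alike. In the Control arm, SOC dressings are in substance the assigned treatment, so the loss is debridement. In the Active arm, the loss is debridement, the secondary dressings of 5.17.3 (which start with a non-adherent contact layer), and any re-application that 5.17.4 would permit. Nor does 6.2.5 say whether an Active subject put on SOC dressings changes them daily, as 5.11 has Control subjects do, or leaves them to the site, as 5.17.3 requires. What is at stake is patient care and fidelity to the randomised regimen.

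**Working it through.** **Which visit is meant.** I read the follow-up visit in 6.2.5 as the unscheduled visit itself. The clause is limited to subjects who have not reached Confirmation, so it cannot mean the 4-week visit.

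**Calendar (Protocol 6.2, 6.2.3, Table 3).** TVk falls nominally on day 7(k−1), ±3 days, counted from randomisation. Confirmation falls c days after closure, with c from 4 to 10 and nominally 7. Re-entry is at TVk+2.

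1. *The plan's own example.* TV9 is day 7×8 = 56, Confirmation is day 56+7 = 63, and TV11 is day 7×10 = 70. Re-entry at TV11 is reproduced, nominally 7 days after Confirmation.
2. *When the bar can apply.* 6.2.5 reserves unscheduled visits for dates outside the next visit window. The Confirmation window opens on day 4 after closure, so the visit falls on day d = 1, 2 or 3.
3. *Time to Confirmation.* c−d is nominally 7−1 = 6, 7−2 = 5 or 7−3 = 4 days. The windows give 4−3 = 1 to 10−1 = 9.
4. *Time to TVk+2.* With a and b the deviations (−3 to +3) of the closure visit and TVk+2, the time is 14+b−a−d. Nominally this is 13, 12 or 11 days; the range is 14−3−3−3 = 5 to 14+3+3−1 = 19. Of the 84 days, 11/84 = 13.1% and 13/84 = 15.5%.

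**What the bar removes.** Under 5.17.3, PriMatrix may go only onto a freshly debrided ulcer. Barring debridement therefore also rules out re-application, even where 5.17.4 would allow it. Table 3 does mark debridement and both treatments in its Unscheduled column, but footnote 2 sends the reader back to 6.2.5 for visits after closure, so the table does not override the bar.

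**The Confirmation Visit, for comparison.** The time from a failed Confirmation to TVk+2 is 14+b−a−c: nominally 14−7 = 7 days, 7/84 = 8.3%, and −2 (taken as 0) to 16 over all windows. In the TV9 example the TV11 window is days 67 to 73. Days 64 to 66 are free for an unscheduled visit, or TV11 can be held on day 67.

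**Closure at TV11.** TV11 is day 70. The Confirmation window is days 74 to 80, identical to the TV12 window (77±3). The re-entry condition that TV12 or TV13 has not been reached can therefore be read two ways. The exit sentence in 6.2.3 names only closures at TV12 or TV13, and the TV9-to-TV11 example extends to TV11-to-TV13. Both favour re-entry at TV13.

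**Rough frequency (assumed, not from the documents).** Take a failed-confirmation rate q of 10% to 20%, first closures spread evenly over TV2 to TV13, the planned closure rates p of 0.46 and 0.26, and 207/2 = 103.5 subjects per arm. Failed confirmations leading to re-entry are p×q/(1−q)×10/12:

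- Active: 4.26% to 9.58%, or 4.4 to 9.9 events.
- SOC: 2.41% to 5.42%, or 2.5 to 5.6 events.

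These count events, and one subject may fail more than once. They cover both routes together; ulcers found open at an unscheduled visit are a subset of unknown size.

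**The case against.** The strongest reply is that 6.2.5 does answer the open ulcer: re-enter the subject and use SOC dressings. The 5.11 procedure for those dressings has the investigator debride if appropriate (step 2) and apply the boot where off-loading is needed (step 8). Section 5.7.3 also lets the investigator treat an infected study ulcer after randomisation. This stands in part. But it sets a general procedure against an explicit statement that debridement is not performed, and it does nothing for the Active regimen.

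It is also fair to say that weekly site care is the norm for Active subjects, that PriMatrix after TV1 is optional, and that the route needs reopening and an unexpected clinic visit within three days. That limits the size.

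Three stronger readings are tempting, and the documents do not support them:

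- *A known-open ulcer must wait for TVk+2.* At Confirmation the text is silent; it does not prohibit care. After a failed Confirmation the subject has re-entered, Section 3.2.2 leaves unscheduled visits for treating the ulcer to the investigator, and the Table 3 Unscheduled column marks debridement and treatment. The 7 days are a nominal gap between scheduled visits.
- *Off-loading is suspended.* Skipping activity 5 omits application and counselling by the site. Sections 5.11 and 5.13 keep the subject in the device.
- *The TV11 wording leaves success or failure to an unblinded site.* The exit sentence and the worked example largely settle it in favour of re-entry.

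Finally, SAP 10.4 records that enrolment was stopped early. Protocol edits can help only subjects still in treatment, if any, and reuse of the text.

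**Conclusion.** The point holds for the unscheduled visit before Confirmation. As written, 6.2.5 bars debridement and arm-assigned treatment for an ulcer the site knows to be open, contradicts 5.9, and takes Active subjects off their regimen. The explicit bar runs nominally 4 to 6 days, to Confirmation; the next visit with listed treatment is nominally 11 to 13 days away. For a closure at TV11 that next visit is TV13, where 6.2.2 gives an open ulcer no debridement or treatment.

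This is a minor matter of patient care and treatment fidelity. It rests on my reading of which visit 6.2.5 means. The documents give no failed-confirmation rate and no frequency for this route, so the counts above are only illustrative. The effect of the delayed care on closure cannot be computed from the documents. No effect on sample size, power, alpha or the primary conclusion is claimed. The gaps at Confirmation and for TV11 closers call for clarification only.

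**What to change.** **Main change, 6.2.5.** Limit the bar on activities 2 to 5 to ulcers that remain closed. If the ulcer is found open before Confirmation, perform activities 2 to 5 with the randomised regimen: SOC per 5.11; for Active, the 5.17.3 secondary dressings changed at the site, with PriMatrix only if 5.17.4 is met. Replace the SOC-dressings sentence accordingly.

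**Clarifications.**
- In 6.2.3 and the Table 3 Confirmation column (Debridement, Control Treatment, Active Treatment, Offloading), state that the same care applies if the ulcer is found open.
- In 6.2.3, state that ulcers first recorded closed at or before TV11 re-enter, with TV11 closers at TV13. Keep the TVk+2 rule and the exit rule for TV12 and TV13 closures.

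No new SAP output is essential: SAP 11.1, 12.1 and 12.2.1 already list closure, all collected data and disposition by subject.

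**Cost.** A few sentences and four table cells, plus a little more site work at visits already held. No extra visits or subjects.
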